6.3.2 Secondary Endpoints

The Secondary Efficacy Endpoints will include:

- Achievement of an IGA score of 'clear' or 'almost clear' PLUS a 2-grade improvement from Baseline at weeks 2 and 4
- Change from Baseline in Overall Assessment of Erythema score at weeks 2, 4, and 8
- Change from Baseline in Overall Assessment of Scaling score at weeks 2, 4, and 8
- Achievement of an Overall Assessment of Erythema (0-3 scale) score of 0 or 1 PLUS a 2-grade improvement from Baseline at weeks 2, 4, and 8
- Achievement of an Overall Assessment of Scaling (0-3 scale) score of 0 or 1 PLUS a 2grade improvement from Baseline at weeks 2, 4, and 8
- Change in WI-NRS pruritus score at weeks 2, 4, and 8, as compared to Baseline
- In subjects with a Baseline WI-NRS pruritus score of ≥4, achievement of a ≥4-point improvement from Baseline in WI-NRS pruritus score at weeks 2, 4, and 8

The binary endpoints will be analyzed using a Cochran-Mantel-Haenszel test stratified by study site and baseline disease severity similar to the primary endpoint.

The continuous endpoints will be analyzed using an analysis of covariance with treatment, study site, baseline disease severity, and baseline value as independent variables. Statistical comparison between the active treatment arm and vehicle arm will be facilitated by using contrasts.

The endpoints measuring change from baseline in overall assessment of erythema and scaling will be statistically tested using CMH row-mean scores test.

6.3.3 Exploratory Endpoints

Exploratory Endpoints will include:

- Change in Scalpdex total score from Baseline at Weeks 2, 4, and 8
- Achievement of an Overall Assessment of Erythema (0-3 scale) score of 0 or 1 at weeks 2, 4, and 8
- Achievement of an Overall Assessment of Scaling (0-3 scale) score of 0 or 1 at weeks 2, 4, and 8
- Achievement of an Overall Assessment of Erythema (0-3 scale) score of 0 at weeks 2, 4, and 8

- Achievement of an Overall Assessment of Scaling (0-3 scale) score of 0 at weeks 2, 4, and 8
- In subjects with a Baseline WI-NRS pruritus score of ≥4, achievement of a ≥4-point improvement from Baseline in WI-NRS pruritus score at weeks 2, 4, and 8
- Change from Baseline in DLQI at weeks 2, 4, and 8
- Change from Baseline in BSA affected at week 8
- A 2-grade improvement in IGA from Baseline

6.4 Safety Evaluation

Descriptive statistics will be calculated for safety data and presented by visit and treatment group for quantitative safety data and frequency counts will be compiled for classification of qualitative safety data. Summaries of local tolerability and pigmentation will be presented by visit and treatment group.

6.4.1 Adverse Events

All treatment-emergent AEs occurring during the study will be recorded and classified on the basis of MedDRA terminology for the safety population. Treatment-emergent AEs are those AEs with an onset on or after the date of study treatment. All treatment-emergent AEs will be summarized by treatment group, the number of subjects reporting treatment-emergent AEs, system organ class, preferred term, severity, relationship, and seriousness.

Serious adverse events (SAEs) will be listed by subject. SAEs will be summarized by treatment group, severity, and relationship to study treatment.

For AEs, each subject will be counted only once within a system organ class or a preferred term using the event with the greatest relationship and greatest severity.

All information pertaining to AEs noted during the study will be listed by subject, detailing the verbatim description given by the Investigator, preferred term, system organ class, start date, stop date, severity, action taken regarding IP, corrective treatment, outcome, and drug relatedness. The event onset will also be shown relative (in number of days) to date of first application. In addition, a listing of subjects who prematurely discontinue from the IP due to adverse events will also be provided.

6.4.2 Local Tolerance Assessments

For both the Investigator's and Subject's assessment of the numeric application site reaction, scores will be summarized individually by using number and percentage of subjects by visit, as well as mean/median scores.

6.4.3 Medical History and Physical Examinations

Medical history for all subjects will be presented in a by-subject listing.

Clinically significant changes observed during physical examination will be captured as adverse

events and included in AE tabulations.

6.4.4 PHQ-8

Data for PHQ-8 will be analyzed by a shift in state of severity using the following scoring system:

- None Minimal depression (0 to 4)
- Mild depression (5 to 9)
- Moderate depression (10 to 14)
- Moderately severe depression (15 to 19)
- Severe depression (20 to 24)

6.4.5 C-SSRS

The C-SSRS will be analyzed per the Columbia–Suicide Severity Rating Scale Scoring and Data Analysis Guide.

6.4.6 Clinical Laboratory Results and Vital Signs/Weight Measurements

All clinical laboratory results and vital signs measurements and their change from baseline (pre-dose), will be summarized by treatment group along with time point of collection.

A shift table summarizing out-of-normal range shifts from baseline by treatment group will be provided for clinical laboratory results.

Shift tables (from baseline) by treatment group will summarize the number of subjects who gain or lose >5% body weight over the course of the study, as well as subjects who gain or lose >10% body weight over the course of the study.

6.4.7 Prior and Concomitant Medications

Prior and concomitant medication information for all randomized subjects will be presented in a by-subject listing. Summary tables by treatment group will be presented by World Health Organization-Anatomical Therapeutic Chemical Classification System (WHO-ATC) therapeutic category and product.

6.5 Patient Reported Outcomes Analyses

6.5.1 WI-NRS

Change from baseline in itch severity will be analyzed by treatment group and over time using the WI-NRS scale. For subjects with WI-NRS pruritus score ≥ 6 at baseline, the proportion of subjects with a 4-point reduction in WI-NRS pruritus score at weeks 2, 4, and 8 as compared to Baseline will be calculated by treatment group and analyzed using a Cochran-Mantel-Haenszel test stratified by study site and baseline disease severity (see secondary endpoints).

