Study Endpoints	 The Primary Efficacy Endpoint will be defined as: Achievement of an IGA score of 'clear' or 'almost clear' PLUS a 2-grade improvement from Baseline at week 8

	The Secondary Efficacy Endpoints will include:
	• Achievement of an IGA score of 'clear' or 'almost clear' PLUS a 2-grade improvement from Baseline
	at weeks 2 and 4
	 Change from Baseline in Overall Assessment of
	Erythema score at weeks 2, 4, and 8
	• Change from Baseline in Overall Assessment of
	Scaling score at weeks 2, 4, and 8
	• Achievement of an Overall Assessment of Erythema
	(0-3 scale) score of 0 or 1 PLUS a 2-grade
	improvement from Baseline at weeks 2, 4, and 8
	• Achievement of an Overall Assessment of Scaling
	(0-3 scale) score of 0 or 1 PLUS a 2-grade
	improvement from Baseline at weeks 2, 4, and 8
	• Change in WI-NRS pruritus score at weeks 2, 4, and
	8, as compared to Baseline
	• In subjects with a Baseline WI-NRS pruritus score
	of \geq 4, achievement of a \geq 4-point improvement from
	Baseline in WI-NRS pruritus score at weeks 2, 4,
	and 8. Exploratory Endpoints will include:
,	 Change in Scalpdex total score from Baseline at
	weeks 2, 4, and 8
	 Achievement of an Overall Assessment of Erythema
	(0-3 scale) score of 0 or 1 at weeks 2, 4, and 8
	 Achievement of an Overall Assessment of Scaling
	(0-3 scale) score of 0 or 1 at weeks 2, 4, and 8
	• Achievement of an Overall Assessment of Erythema
	(0-3 scale) score of 0 at weeks 2, 4, and 8
	• Achievement of an Overall Assessment of Scaling
	(0-3 scale) score of 0 at weeks 2, 4, and 8
	• In subjects with a Baseline WI-NRS pruritus score
	of \geq 4, achievement of a \geq 4-point improvement from
	Baseline in WI-NRS pruritus score at weeks 2, 4,
	and 8
	• Change from Baseline in DLQI at weeks 2, 4, and 8
	• Change from Baseline in BSA affected at week 8
	• A 2-grade improvement in IGA from Baseline

Statistical Considerations:	There are approximately 184 subjects planned for this study; randomized 2:1 to ARQ-154 foam 0.3% : vehicle
	QD, stratified by study site and baseline disease severity.
	A sample size of 184 subjects will provide approximately 90% power to detect an active response of at least 55.8%, assuming 159 (86%) subjects complete the study and a vehicle response of 30%, based on two-group X^2 test of equal proportions (without continuity correction, using a 2-sided alpha of 0.10).

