6.1 Statistical Methods

The methodology presented below is a summary of the more detailed analysis plan that will be presented in the Statistical Analysis Plan (SAP). The SAP will be finalized before the database is locked and unblinded. Any changes to the methods described in the final SAP will be described and justified in the clinical study report.

All statistical processing will be performed using SAS[®] (Version 9.4 or later) unless otherwise stated.

Descriptive statistics will be used to provide an overview of the efficacy, safety and pharmacokinetic results. For categorical parameters, the number and percentage of subjects in each category will be presented. The denominator for percentage will be based on the number of subjects appropriate for the purpose of analysis. For continuous parameters, descriptive statistics will include n (number of subjects), mean, standard deviation (SD), median, minimum, and maximum.

P-values of less than 0.10 will be considered statistically significant based on a two-sided test unless otherwise specified. No adjustments for multiplicity are planned.

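### Section 6.5.1 analyses the itch-responder endpoint in subjects with baseline WI-NRS of at least 6, but every endpoint list defines it for baseline of at least 4

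*Protocol*

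**What the plan says.** The endpoint is defined in section 6.3.2 as "In subjects with a Baseline WI-NRS pruritus score of ≥4, achievement of a ≥4-point improvement from Baseline", assessed at weeks 2, 4 and 8. The same bullet stands in section 6.3.3 as an exploratory endpoint. The synopsis also carries it twice, once in the secondary list and once in the exploratory list, each time with a baseline threshold of 4.

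For the test, section 6.3.2 states: "The binary endpoints will be analyzed using a Cochran-Mantel-Haenszel test stratified by study site and baseline disease severity similar to the primary endpoint".

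Section 6.5.1 then describes a responder analysis of the same scale. It begins "For subjects with WI-NRS pruritus score ≥ 6 at baseline", evaluates "the proportion of subjects with a 4-point reduction in WI-NRS pruritus score at weeks 2, 4, and 8 as compared to Baseline", and assigns a "Cochran-Mantel-Haenszel test stratified by study site and baseline disease severity (see secondary endpoints").

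Section 5.2.5 announces a responder analysis based on a 4-point reduction and gives no baseline threshold. Section 6.1 describes the statistical section as a summary of the SAP and adds: "The SAP will be finalized before the database is locked and unblinded".

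**The concern.** A responder endpoint restricted by a baseline score is defined partly by that restriction, because it fixes who is in the denominator. Here the endpoint lists and the analysis text fix it differently, so an analyst could cite the protocol for either population.

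The subjects in dispute are those with a baseline of 4 or 5. On a 0 to 10 scale they have little room to respond. From 4, an improvement of at least 4 points means reaching 0. From 5, it means reaching 0 or 1. Leaving them out therefore reduces n and may also change the response rate in each arm and the difference between arms. The protocol does not allow the direction or size of that change to be predicted. If the choice stays open, a reader of the results could not tell which analysis had been prespecified.

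**Working it through.** **Step 1: set the statements side by side.**

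| Place in the protocol | Baseline WI-NRS | Response | Visits | Test |
|---|---|---|---|---|
| Synopsis, secondary list | ≥4 | ≥4-point improvement | weeks 2, 4, 8 | as for the primary endpoint (stratified CMH) |
| Synopsis, exploratory list | ≥4 | ≥4-point improvement | weeks 2, 4, 8 | not stated |
| 6.3.2 | ≥4 | ≥4-point improvement | weeks 2, 4, 8 | CMH by site and baseline severity |
| 6.3.3 | ≥4 | ≥4-point improvement | weeks 2, 4, 8 | not stated |
| 5.2.5 | none given | 4-point reduction | not stated for the responder analysis | not stated |
| 6.5.1 | ≥6 | 4-point reduction | weeks 2, 4, 8 | CMH by site and baseline severity |

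**Step 2: ask whether 6.5.1 could be a different analysis.** It shares the instrument, the size of change, the visits and the test with 6.3.2, and it refers the reader to the secondary endpoints. That reference leads to a definition with a threshold of 4. No endpoint list contains a threshold of 6, and 6.5.1 does not call itself a subgroup or supplementary analysis. It therefore reads as the analysis of the secondary endpoint in a different population.

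**Step 3: look for a figure to reproduce.** There is none. The protocol gives no sample size, power or expected response rate for this endpoint, and no mean, SD or distribution of baseline WI-NRS.

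**Step 4: illustrate the possible size, on assumptions only.** Suppose baseline WI-NRS is a rounded normal variable with mean m and SD s, restricted to the integers 0 to 10:

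P(k) = [Φ((k + 0.5 − m)/s) − Φ((k − 0.5 − m)/s)] / [Φ((10.5 − m)/s) − Φ((−0.5 − m)/s)]

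The share of qualifying subjects kept by 6.5.1 is P(≥6)/P(≥4). The number with baseline 4 or 5 among the 184 planned subjects is 184 × [P(≥4) − P(≥6)].

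| Assumed mean, SD | P(≥4) | P(≥6) | Share kept | Share dropped | Baseline 4 or 5, of 184 |
|---|---|---|---|---|---|
| 5, 2 | 0.775 | 0.401 | 0.52 | 48% | 69 |
| 5, 2.5 | 0.732 | 0.418 | 0.57 | 43% | 58 |
| 6, 2 | 0.894 | 0.594 | 0.66 | 34% | 55 |
| 6, 2.5 | 0.839 | 0.566 | 0.67 | 33% | 50 |
| 7, 2 | 0.958 | 0.764 | 0.80 | 20% | 36 |
| 7, 2.5 | 0.913 | 0.703 | 0.77 | 23% | 39 |

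For the first row: 0.401/0.775 = 0.52, and 184 × (0.775 − 0.401) = 69. Using the normal density at the integers instead of interval probabilities gives 0.51 for that row, or 49% dropped, so the discretisation matters little.

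**The case against.** The strongest reply is that the endpoint is already complete without 6.5.1. Section 6.3.2 gives the definition and the test together, all four list entries agree on 4, and the one sentence that differs sends the reader back to them. On that view a careful SAP author would use 4, and the SAP, which was not available for this review, may already do so. This stands in part: it makes 4 the better-supported reading and narrows the ambiguity. It does not remove the conflict. The protocol then has two analysis statements for one endpoint with different denominators, which is a contradiction rather than detail deferred to the SAP.

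A second reply is that the documents do not prove which threshold was intended. The identical bullet appears under both secondary and exploratory endpoints, so one of the two may have been meant to carry a threshold of 6. That is possible. The sponsor should confirm this before a duplicate is deleted.

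Third, the consequence is limited. This is one of several secondary endpoints in a Phase 2a proof-of-concept trial with no multiplicity adjustment, nothing else depends on it, and WI-NRS is collected in a way that permits either analysis. This stands, and it keeps the point below the level of a critical error. The numerical illustration rests on assumed inputs and carries no weight in that judgement.

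**Conclusion.** The concern holds. One named secondary endpoint has two incompatible analysis populations in the current protocol: baseline of at least 4 in every list that defines it, and at least 6 in the section describing its analysis. This should be corrected before unblinding.

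The conflict rests on the text alone and needs no assumption. Its numerical effect is unknown. The range of about 20% to 48% of qualifying subjects dropped depends entirely on an assumed baseline mean of 5 to 7 and SD of 2 to 2.5. The primary endpoint, the sample size and the WI-NRS change-from-baseline endpoint are unaffected.

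**What to change.** Change the sentence in 6.5.1 to a baseline WI-NRS of at least 4 and an improvement of at least 4 points, matching 6.3.2 and the synopsis, and carry the same definition into the SAP. If the sponsor also wants an analysis at 6 or more, state it separately and label it supplementary.

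As an editorial clean-up, list the endpoint once, as secondary, and remove the duplicate from 6.3.3 and from the synopsis exploratory list, after confirming that neither duplicate was meant to carry a different threshold. The response wording in 5.2.5 can be aligned at the same time.

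The cost is one sentence and two deleted bullets, plus the optional wording change in 5.2.5. Data collection, visits and sample size do not change. The correction must precede unblinding. Because 6.1.3 gives some sponsor staff interim results from the first 60 subjects, and does not say whether these include itch data, making it before that analysis would be cleaner.

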6.5.2 Dermatology Life Quality Index (DLQI)

Change from baseline in DLQI total score will be analyzed at weeks 2, 4, and 8 using an analysis of covariance with treatment, baseline score, and the stratification factors as independent variables.

6.5.3 Scalpdex

The Scalpdex will be analyzed as change from Baseline in total score as assessed at weeks 2, 4, and 8 using an analysis of covariance with treatment, baseline score, and the stratification factors as independent variables.

6.6 Pharmacokinetic Analysis

Plasma drug concentrations at pre-dose will be summarized using descriptive statistics.

For all subjects, blood samples for the determination of roflumilast and its N-oxide metabolite will be collected at scheduled time points as delineated in the Schedule of Visits and Assessments (Section 1.3).

A manual for blood sampling, collection, processing, and sample shipment will be provided in a separate document.

7 STUDY ADMINISTRATION

7.1 Ethics

7.1.1 Ethics Review Board

Before enrollment of patients into the study, the current protocol, ICF, and any accompanying material to be provided to the subjects will be reviewed and approved by an appropriate IRB or IEC, as required by FDA (21 CFR § 56), Health Canada, and ICH GCP regulations. A letter documenting the IRB or IEC approval must be received by the Sponsor before the initiation of the study at a clinical site. Amendments to the protocol will be subject to the same requirements as the original protocol.

The Investigator, Sponsor, or designee will submit a progress report at least once yearly to the IRB or IEC. However, the frequency of these reports will depend on IRB or IEC requirements. As soon as possible after completion or termination of the study, the Investigator will submit a final report to the IRB or IEC per the IRB or IEC requirements, and in compliance with FDA and Health Canada regulations and ICH GCP guidelines.

The Investigator, the Sponsor, or designee shall promptly notify the IRB or IEC of any SAEs, SUSARs, or any other information that may affect the safe use of the IP during the study, per the IRB or IEC local requirements, and in compliance with FDA and Health Canada regulations and ICH GCP guidelines.

7.1.2 Ethical Conduct of the Study

This research will be carried out in accordance with the protocol, the principles of the Tri-Council Policy Statement (TCPS), the ethical principles set forth in the Declaration of Helsinki, and the ICH harmonized tripartite guideline regarding GCP (E6 Consolidated Guidance, April 1996).

7.1.3 Subject Information and Consent

The Investigator is responsible for obtaining written informed consent from each individual participating in this study after adequate explanation (in non-technical terms) of the purpose of the study, the procedures to be carried out and the potential hazards before undertaking any study-related procedures. The Investigator must use the most current approved consent form for documenting written informed consent. Subjects will be assured that they may withdraw from the study at any time without jeopardizing their medical care. Each informed consent will be read, appropriately signed and dated by the subject, the Investigator conducting the consent discussion, and by an impartial witness if required by local requirements.

Subjects will be given a signed copy of their ICF.

7.2 Study Completion and Termination

7.2.1 Study Completion

The study is considered completed with the last visit of the last subject participating in the study. The final data from the investigational site will be sent to the Sponsor (or designee) after completion of the final subject visit at that site, in the time frame specified in the Clinical Trial Agreement.

7.2.2 Study Termination

The Sponsor reserves the right to close the investigational site or terminate the study at any time for any reason at the sole discretion of the Sponsor. Investigational sites will be closed upon study completion. An investigational site is considered closed when all required documents and study supplies have been collected and a site closure visit has been performed. The Investigator may initiate site closure at any time, provided there is reasonable cause and sufficient notice is given in advance of the intended termination.

Reasons for the early closure of an investigational site by the Sponsor or Investigator may include but are not limited to:

- Failure of the Investigator to comply with the protocol, the Sponsor's procedures, or GCP guidelines.
- Inadequate recruitment of subjects by the Investigator.
- Discontinuation of further IP development

7.3 Study Monitoring

Prior to the initiation of the clinical investigation, Sponsor representatives or designees will visit the clinical site where the investigation is to be conducted. Sponsor representatives or designees shall ensure that the Investigator understands the investigational status of the investigational product, all requirements of the investigation to be undertaken, and all of his/her responsibilities as an Investigator. Sponsor representatives or designees will also visit the clinical site at appropriate intervals as required to ensure compliance with the protocol and to verify the accuracy and completeness of data reported on the CRFs. The Study Director or designees shall be available for consultation with the Investigator and serve as liaisons between the clinical site and the Sponsor.

The Sponsor or authorized designees may inspect all documents and records required to be maintained by the Investigator, including but not limited to medical records (office, clinic, or hospital) and investigational product dispensation logs for the subjects in this clinical investigation. The Investigator must permit access to such records. The Investigator must obtain, as part of informed consent, permission for an authorized representative of the Sponsor, or regulatory authorities, to review, in confidence, any records identifying subjects.

7.4 Data Quality Assurance

In order to ensure the collection of accurate, consistent, complete, and reliable data during this clinical investigation, Sponsor representatives or designees may conduct audits of participating sites at appropriate intervals throughout the study. The results of these periodic site audits may be subject to review by independent auditors at completion of the clinical investigation. The Clinical Study Report will be audited by the Premier Research's Quality Assurance (QA) department and the QA audit certificate will be included in the study report.

All clinical data will undergo a 100% quality control check prior to clinical database lock. Edit checks are then performed for appropriate databases as a validation routine to check for missing data, data inconsistencies, data ranges etc. Corrections are made prior to database lock.

